Approved by the FDA in 2011, Exparel (liposomal bupivacaine) is a sustained-release version of the local anesthetic bupivacaine. While bupivacaine may last 6 to 12 hours to provide post-surgical relief, it is claimed that Exparel can last up to 72 hours after local infiltration at the surgical site [14]. Different studies have also compared the efficacy of Exparel to bupivacaine for the management of postsurgical pain following various surgical procedures, including inguinal hernia repair, breast augmentation, and TKA [15-20]. While some of these studies have supported the efficacy of Exparel to provide superior relief of postsurgical pain, others have found bupivacaine to be just as effective [20]. There is still however, a paucity of literature on the efficacy of Exparel for spine surgery pain management.

Study Questions/Objectives and Hypothesis

This study is aimed at prospectively examining clinical and economic outcomes when managing postsurgical pain using local infiltration of Exparel for patients undergoing primary, 1 or 2 level, lumbar laminectomy with or without fusion. There is a growing body of evidence suggesting that combining Exparel with a short acting numbing medicine gives much better pain coverage. The rationale is that Exparel can take several hours to have anesthetic onset and conventional thinking believes that if we can cover the immediate postoperative pain better with an immediate acting anesthetic to bridge the onset gap, then better outcomes will be achieved. The combination of these medications have been used in various studies previously in other areas of the body both in orthopedics and non-orthopedics and no adverse effects of combining these medications and in similar quantities/dosing have been observed [22,23,24]. To this end, we hypothesize that compared to patients that only received local infiltration of bupivacaine or only administered Exparel, the intervention group treated to a combination of Exparel and bupivacaine would, during their hospital stay following surgery, experience:

- 1. Reduced mean postoperative pain score (Wong-Baker pain faces scale of 0-no pain, to 10-extreme pain)
- 2. Reduced total consumption of opioids (in mean morphine equivalents)
- 3. Reduced overall cost of postoperative pain control medications
- 4. Decreased incidence of ORAEs

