- 5. Reduced time to achieve physical therapy discharge criteria (criteria set according to each patient's living situation, preoperative physical function, comorbidities, and other goals)
- 6. Reduced inpatient length of stay (LOS)

Study Benefits to Virtua

This study could potentially benefit Virtua in several ways. If Exparel is shown to reduce postoperative pain for spine surgery patients, and consequently reduce their opioid consumption for postoperative pain management, then there could be the potential to see an improvement in patient satisfaction with regards to pain management. In addition, Virtua could stand to gain some cost savings if Exparel is shown to support decreased incidence of ORAEs such as respiratory depression, leading to reduced time to physical therapy discharge criteria and consequently reduced LOS.

If on the other hand, the study indicates that the more expensive Exparel is no more effective at managing postoperative pain compared to the cheaper alternatives, then Virtua stands to directly gain significant cost savings by adopting the use of the cheaper options as standard practice.

Study Methodology

Patients who meet all of the following inclusion criteria may be eligible to participate in the study if:

- 1. Age 18 or older;
- 2. Primary indication is low back pain, lumbosacral radiculopathy, lumbar disc degeneration, lumbar disc herniation, stenosis, spondylolisthesis, spondylolysis, or deformity requiring surgical intervention;
- 3. Scheduled to undergo primary, 1 or 2 level, posterior lumbar laminectomy with or without fusion, discectomy with fusion, or fusion at Virtua Memorial Hospital;
- 4. Willing to provide informed consent, participate in study, and comply with study protocol.

Patients who meet any of the following criteria may not be eligible to participate:

- 1. Hypersensitivity or allergy to local anesthetics;
- 2. Pregnant or contemplating pregnancy prior to surgery;
- 3. Previous surgery in lumbar spine (i.e. other than microdiscectomy);
- 4. Prior treatment for alcohol, recreational drug, or opioid abuse;
- 5. Serious spinal conditions (e.g. spinal cord compression, cauda equina syndrome, spinal infection, spinal tumor, spinal fracture, inflammatory or systemic spinal arthritis);
- 6. Surgery involving more than 2 vertebral levels;

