Secondary outcome measures in this study include total opioid consumption. All opioid analgesics used in the hospital will be recorded in the participant's clinical record, including: Name of medication (e.g. morphine); Dose administered (e.g. 10mg); Route of administration (e.g. IV, IM, oral); Reason for administration (e.g. surgical site pain). All opioid analgesics will be converted into oral mg morphine equivalent to determine the total dose of opioids used during the hospital stay using the conversion factors in Appendix 2. Other secondary outcome measures include mean time to achieve physical therapy discharge criteria, mean LOS, and incidence of ORAEs. ORAEs will be documented using the checklist shown in Appendix 3 with assistance from a nurse during every nursing shift (i.e. every 12 hours) until hospital discharge).

Means will be compared among all the three arms using analysis of variance, proportions will be compared using chi-square tests, and logistic regression will be used to analyze for confounding effects. All statistical analyses will be conducted in Minitab 16 Statistical Software.

Protection of Human Subjects

Throughout the study, the principal investigators (Virtua Memorial spine surgeons and PAs), will be the only ones with access to the data collection database. Following the completion of the study, all personal health information collected, including name, gender, age, significant medical comorbidities, and postoperative complications, will be de-identified as soon as possible prior to data analysis and any subsequent publications or research submissions. Patient would be told participation is purely voluntary with no monetary reimbursement and minimal risk of being assigned to one of the three pain management groups.

References

- 1. Centers for Disease Control and Prevention (CDC). National Hospital Discharge Survey: 2006 Annual Summary. Vital and Health Statistics, 2010;13(168).
- 2. Centers for Disease Control and Prevention (CDC), Health, United States, 2012: With Special Features on Emergency Care. 2012: Hyattsville, MD.

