APPENDIX 3. INCIDENCE OF OPIOID RELATED ADVERSE EVENTS

Instructions

Please indicate if you have experienced any of the following symptoms in the past 12 hours:

Symptom	Yes	No	Comments
Constipation			
Falling			
Нурохіа			
Lethargy			
Nausea			
Postoperative ileus			
Respiratory depression			
Sedation			
Somnolence			
Unsteadiness			
Urinary retention			
Vomiting

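### The opioid adverse event checklist is worded as patient recall but includes events that staff measure or diagnose, with no definitions and no defined nurse role

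*Combined protocol and SAP*

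**What the plan says.** The fourth hypothesis in Study Questions/Objectives and Hypothesis is "Decreased incidence of ORAEs", with no event ranked above another. Study Benefits to Virtua links expected savings to "decreased incidence of ORAEs such as respiratory depression". That is the only ORAE it names.

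For measurement, Study Methodology states that "ORAEs will be documented using the checklist shown in Appendix 3", completed "with assistance from a nurse during every nursing shift (i.e. every 12 hours) until hospital discharge". No other source is named for this outcome. The contrast with other outcomes is plain. Pain scores come from nursing entries in the clinical record, and for opioid use "All opioid analgesics used in the hospital will be recorded in the participant's clinical record".

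Appendix 3 opens with "Please indicate if you have experienced any of the following symptoms in the past 12 hours". It lists twelve items with columns for Yes, No and Comments. The items include "Respiratory depression" and "Postoperative ileus", as well as hypoxia, sedation, somnolence and lethargy. No item has a definition, threshold or scale. Proportions are to be compared by chi-square test.

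**The concern.** The form asks patients to report, as symptoms, things that a patient does not directly observe. Low oxygen saturation is a reading, respiratory depression is an observation by staff, and ileus is a diagnosis. Where the problem is drowsiness, the person asked is also the person least able to answer. If a blank or a vague answer becomes a No, the event is lost.

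The outcome at stake is a stated hypothesis. Respiratory depression, the single event used to illustrate the expected benefit, is among the items that recall suits least. The Background section places the highest ORAE risk in the first 24 hours, when opioid use peaks. At one checklist per 12 hours, that is 24 / 12 = 2 checklists, completed when self-report is likely to be weakest.

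**Working it through.** **1. Who can report what.** This sorting of the twelve Appendix 3 items is a judgement, since the form makes no such distinction.

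| Group | Items | Count |
|---|---|---|
| Suited to patient report | nausea, vomiting, constipation, unsteadiness, falling | 5 |
| Measured or diagnosed by clinicians | hypoxia, respiratory depression, postoperative ileus | 3 |
| Overlapping drowsiness items | lethargy, sedation, somnolence | 3 |
| Partly reportable | urinary retention | 1 |

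Total: 5 + 3 + 3 + 1 = 12.

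**2. Instruction against method.** Appendix 3 puts the question to the patient. Study Methodology adds help from a nurse. Neither says whether the nurse reads the items aloud, enters what was seen on the shift, or consults the chart. Two nurses could follow the plan faithfully and record the same desaturation differently. Neither text says what to enter when the patient cannot answer.

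**3. Direction of the effect.** Let p1 and p2 be true event proportions in two arms, and let the form have sensitivity Se and specificity Sp, equal in both arms. Then

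observed difference = (Se + Sp − 1) × (p1 − p2).

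Missed events (Se below 1) and over-called events (Sp below 1) both shrink the difference. Unequal capture is not needed.

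**4. Size.** The plan gives no ORAE rate, target difference or power, so there is no figure of its own to reproduce. Its one sample-size calculation concerns the pain score and has no bearing here. The table is therefore an illustration. Event rates and capture rates are assumed, Sp = 1, n = 45 per arm (the planned enrolment), and the test is one pairwise comparison at two-sided 0.05:

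power = Φ{ [ |p1 − p2| − 1.96 √(2p̄(1 − p̄)/n) ] / √[ (p1(1 − p1) + p2(1 − p2))/n ] }.

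For 30% v 10% fully captured: (0.20 − 0.1653)/0.0816 = 0.425, power 0.665. At 40% capture the observed rates are 12% v 4%: (0.08 − 0.1121)/0.0566 = −0.567, power 0.285.

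Observed difference in points, with power in brackets:

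| True rates | Capture 100% | 80% | 60% | 40% | 50% in the higher-rate arm, 80% in the other |
|---|---|---|---|---|---|
| 50% v 25% | 25 (0.694) | 20 (0.545) | 15 (0.397) | 10 (0.262) | 5 (0.082) |
| 30% v 10% | 20 (0.665) | 16 (0.545) | 12 (0.416) | 8 (0.285) | 7 (0.178) |
| 10% v 3% | 7 (0.268) | 5.6 (0.221) | 4.2 (0.175) | 2.8 (0.129) | 2.6 (0.095) |

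For 30% v 10%, the last column is 30 × 0.5 − 10 × 0.8 = 15 − 8 = 7 points. Equal 50% capture would leave 15 − 5 = 10. So low capture alone removes 10 of the 20 points, and unequal capture removes a further 3.

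The bottom row rests on very few events (45 × 0.03 = 1.35 expected in one arm), so the normal approximation there is rough.

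**The case against.** The strongest reply is that a nurse takes part at every shift. That nurse may well know of a desaturation treated during the shift and has a Comments column to note it. Patients and ward staff are blinded, so knowledge of the arm should not drive reporting. Protection of Human Subjects also lists postoperative complications among the data collected, so a serious event might be held elsewhere in the study data. The outcome is secondary, and the primary pain outcome is untouched.

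Much of this stands. A reader might infer that ORAEs rest on patient recall alone. The documents do not show that; they leave the nurse's role open. A reader might also conclude that these events will be under-recorded. That is a possibility only, because undefined items can be over-called too: one drowsy patient can be marked for lethargy, sedation and somnolence. If the analysed proportion is patients with any ORAE, triple marking would not change it, but the plan does not say how the proportion is formed.

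The reply does not close the gap. The plan nowhere tells the nurse to enter charted or observed events, and the form's wording points the other way. Complications data are not linked to ORAE incidence. Blinding does not protect against reporting impaired by opioid exposure itself, which the trial expects to differ between arms.

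**Conclusion.** The point holds as a measurement gap in a secondary outcome. The only named ORAE source is worded as 12-hour patient recall. It includes at least three clinician-assessed events and three overlapping drowsiness items, all undefined. The nurse's role is unspecified, and no rule covers a patient who cannot answer. Events may be missed or recorded inconsistently, most likely in the first 24 hours, and this would tend to dilute a between-arm difference.

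The size cannot be taken from the documents. The figures above rest on assumed event and capture rates and show direction and a plausible range only.

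Two further readings should be resisted. Counting seven of the twelve items as unsuited to self-report is an upper count, since patients can partly report drowsiness and difficulty passing urine. Nor do the documents show that these are the events the plan most wants to reduce: respiratory depression appears once, as an example, and the hypothesis covers all ORAEs alike.

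**What to change.** Revise Appendix 3 and the matching sentence in Study Methodology before enrolment:

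- Keep patient report for nausea, vomiting, constipation, unsteadiness and falls.
- Have the same blinded shift nurse complete hypoxia, respiratory depression, postoperative ileus and urinary retention from the clinical record, with one sedation rating in place of lethargy, sedation and somnolence.
- Agree outcome definitions for these items in advance and print them on the form.
- State that a shift in which the patient cannot answer is completed from the record and not left blank.
- Report the chart-based items alongside the patient-reported ones. A separate test of the chart-based items is optional, and events may be sparse at 45 per arm.

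The cost is a reworded form, agreement on definitions, and a little more nurse charting time per shift. No extra staff, visits or patients are needed. The documents do not say where the infiltrated drug is charted, so the form should direct the nurse to ward observations and notes, to protect blinding.

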On the day of surgery, in the operating room, the circulating nurse will roll a die to randomly assign the patient to one of the three pain management groups. The study intervention group (die roll outcome 1 or 2) will receive a local infiltration of EXPAREL and bupivacaine 0.5% w/v solution into the surgical site (1 level patients – 20 mL Exparel + 30 mL bupivacaine 0.5% w/v solution; 2 level patients – 20 mL Exparel diluted to 40mL + 30 mL bupivacaine 0.5% w/v solution). The two medications will not be combined in the same syringe to minimize the possibility of a direct interaction between the two. While to date, no such interaction has been confirmed, we will maintain a strict "no mixing of bupivacaine and Exparel in the same syringe" policy throughout this study. The second group (die roll outcome 3 or 4) will only be administered local infiltration of Exparel (1 level patients – 20 mL Exparel; 2 level patients – 20 mL Exparel diluted to 40 mL). The third group will be treated to a local infiltration of 30 mL bupivacaine 0.5% w/v solution. Anesthesiologists will use their usual pre-operative and intra-operative techniques for all study participants and both study groups will receive nurse-administered rescue opioids as needed.

The patients and all staff, including hospital nursing staff, case management, and physical therapists, will be blinded as to which pain management treatment the patient received. While the surgical team cannot be blinded because the appearance of the drugs is different, they will however, not be assessing the outcome measures.

The primary outcome in this study will be the mean postoperative pain score derived from the pain scores recorded by the nursing staff in each participant's clinical records using the visual analog scale of 0-no pain to 10-extreme pain, several times in each 24-hour period, for the entire duration of the patient's hospital stay. Adopting [20] assumptions of a target reduction in mean overall postoperative pain scores of 1 point on the VAS and our anticipated variance of 2, it is estimated using one-way analysis of variance that for a statistical power of 80% and significance level of 0.05, a minimum of 40 participants will be required in each study group for a total of 120 study participants. To minimize the possibility of dropouts or incomplete data impacting the analysis, a minimum of 45 participants will be enrolled in each study group, for a total of 135 enrollees.

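### The only planned comparison of means is an omnibus three-arm ANOVA, which cannot by itself establish that the combination beats bupivacaine alone and Exparel alone; no contrast or success rule is stated

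*Combined protocol and SAP*

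**What the plan says.** All references are to the combined protocol and SAP.

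- **Study Questions/Objectives and Hypothesis.** The combination group is expected to have a reduced mean pain score "compared to patients that only received local infiltration of bupivacaine or only administered Exparel". The hypothesis is directional and names two comparators.
- **Study Methodology, sample size.** The calculation takes "a target reduction in mean overall postoperative pain scores of 1 point on the VAS and our anticipated variance of 2", and "it is estimated using one-way analysis of variance that for a statistical power of 80% and significance level of 0.05" 40 participants per group are needed. Enrolment is then raised: "a minimum of 45 participants will be enrolled in each study group, for a total of 135 enrollees". The pair or pairs of arms that differ by 1 point are not stated.
- **Study Methodology, analysis.** "Means will be compared among all the three arms using analysis of variance". The rest of the sentence covers other matters: "proportions will be compared using chi-square tests, and logistic regression will be used to analyze for confounding effects". Neither of those methods contrasts mean pain between arms.

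No section names a contrast, a follow-up step after F, a multiplicity method, or a rule on whether the combination must beat one comparator or both.

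**The concern.** The omnibus F is non-directional. It rejects for any pattern of unequal means, including one in which only Exparel alone and bupivacaine alone differ, or one in which the combination adds nothing to Exparel. Following the plan exactly therefore does not answer the trial's own question.

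Such patterns are plausible. The background reports that some studies favoured Exparel over bupivacaine while "others have found bupivacaine to be just as effective". If Exparel is better here and added bupivacaine contributes nothing, the F test will tend to be significant without the combination beating Exparel.

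The section Study Benefits to Virtua links the result to purchasing, in case "the more expensive Exparel is no more effective at managing postoperative pain compared to the cheaper alternatives". That decision rests on particular pairwise differences with intervals, which F does not supply. If the success rule is chosen after the data are seen, the choice can settle the conclusion.

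**Working it through.** **Inputs from the plan:** 3 arms, difference 1 point, variance 2, alpha 0.05, power 80%, n = 40 per arm (45 enrolled).

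**Assumptions, because the plan gives none:** the pattern of the three means (written below as points above the lowest arm), two-sided contrast tests, and a pooled variance from the three-arm model.

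**1. Reproduce the plan's 40 per arm.** Power of the F test uses the noncentral F with 2 and 3(n − 1) degrees of freedom and noncentrality λ = n Σ(μᵢ − μ̄)² / σ².
- Means 0 / 0.5 / 1: Σ = 0.25 + 0 + 0.25 = 0.5, so λ = 40 × 0.5 / 2 = 10. Power is 80.5% at n = 40 and 79.4% at n = 39, so 40 is the smallest n reaching 80%.
- Means 0 / 1 / 1 would need only 30 per arm.

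The stated size is thus reproduced for an omnibus F with the third arm midway. That pattern is inferred, not stated.

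**2. What a significant F shows if the combination adds nothing to Exparel.** Combination = Exparel, bupivacaine higher by δ: Σ = 2δ²/3. For δ = 1, λ = 40 × 0.667 / 2 = 13.33.

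| δ (points) | F rejects, 40/arm | F rejects, 45/arm |
|---|---|---|
| 1 | 90.8% | 93.9% |
| 0.75 | 67.6% | 73.2% |
| 0.5 | 34.5% | 38.5% |

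In every row the combination is declared better than Exparel in about 2.5% of trials if that contrast is tested at two-sided 0.05 without a gate. At δ = 1, by simulation, the combination beats both comparators in 2.5%. It beats at least one, after a significant F, in 85.3% (89.5% at 45 per arm).

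**3. Power of the two hypothesised contrasts** (simulation, each at two-sided 0.05).

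| Means: combination / others | Both won, 40/arm | Both won, 45/arm |
|---|---|---|
| 0 / 1 / 1 | 80.3% | 85.5% |
| 0 / 0.5 / 1 | about 34% | about 38% |

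**4. Power for one 1-point contrast at 40 per arm, if one win is enough.**
- Bonferroni (0.025 each): about 81%, whatever the third mean.
- Holm: about 86% when both advantages are 1 point.
- F as a gate, then 0.05: 85.3% when the third arm ties with either of the other two, 79.7% when it is midway.

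**5. Error with all three means equal, two combination contrasts at 0.05, 40 per arm.**

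| Event | Not gated on F | Gated on F |
|---|---|---|
| Combination falsely declared better than at least one | about 4.5% | about 2.1% |
| False difference in either direction | 9.0% | 4.2% |

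**6. Precision.** 95% CI half-width = t × √(2 × 2 / n) = 1.980 × √0.1 = 0.63 point at n = 40 (0.59 at n = 45).

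**The case against.** The strongest reply is that the intended claim is clear enough. The title and the hypothesis set the combination against both single drugs, so the ordinary reading is better than each. On that reading no alpha split is needed, and 40 per arm gives about 80% joint power if the 1-point advantage holds against each. Pairwise comparison after an ANOVA is also routine. This stands in part: it limits the defect to wording and a restated power claim. It does not remove it, because the plan states neither the rule nor the follow-up, and routine follow-up would not say whether one win suffices.

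Three stronger readings are tempting, and the documents do not support them.

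- *The sample size is wrong.* It is not: 40 per arm is reproduced for the test the plan names.
- *The gap between 85.3% and 2.5% is a false-positive rate.* It is not. In that scenario the combination truly is 1 point better than bupivacaine, so declaring that win is correct. Only extending it to Exparel would be an error, and nothing in the plan says that would be done.
- *False success is inflated to 9% or more.* The 9.0% counts false differences in both directions. The hypothesis is directional, and on that scale the ungated figure is about 4.5%.

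The 1-point target is also adopted from a cited knee arthroplasty study. Whether that source ties it to a pair of arms cannot be checked here; the plan's own text does not.

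**Conclusion.** The point holds and should be fixed. The planned omnibus F does not test the stated hypothesis: at 40 per arm it can reject in 90.8% of trials while the combination beats both single drugs in only 2.5%. That size depends on the assumed pattern (combination equal to Exparel, both 1 point below bupivacaine) and falls to 34.5% rejection if the gap is 0.5 point. The true gap is unknown.

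The 80% power statement is attached to no particular claim. The same 40 per arm gives 80.5% for the omnibus F with a midway arm, about 80% for beating both comparators by 1 point each, or about 34% for beating both when one comparator is midway. All figures assume the plan's variance of 2, equal arms and complete data.

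**What to change.** Add to the analysis paragraph of Study Methodology, before any results are seen:

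1. **Two primary contrasts** from the same ANOVA model: combination minus bupivacaine alone, and combination minus Exparel alone, each with a 95% CI.
2. **The success rule, with matching error control.**
   - If the claim is better than each: both contrasts at two-sided 0.05, with no alpha split. The chance of falsely declaring the combination better than both is at most 2.5%.
   - If one win is enough: Bonferroni, Holm, or the planned F kept as a gate before the two 0.05 contrasts. The gate is not uniformly the stronger choice; with a midway third arm it falls just below Bonferroni (79.7% against about 81%). The report should name which comparator was beaten.
3. **Exparel alone versus bupivacaine alone**, with a CI, as a supportive comparison, since the purchasing question depends on it.
4. **In the sample-size paragraph**, the assumed pattern of means and the claim to which the 80% refers.

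The cost is a few sentences and a restated power figure; no extra patients or data are proposed. The downside is that the restated power may look less favourable: if both must be won and one comparator is thought to be intermediate, the team would have to report about 34% at 40 per arm.

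### Low-priority improvement: the ANOVA of mean pain score is valid but leaves out planned number of levels (1 or 2), a cheap pre-randomisation covariate with a small, conditional gain

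*Combined protocol and SAP*

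**What the plan says.** All the relevant text is in the combined protocol and SAP, under Study Methodology.

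- **Analysis.** The comparison of means is covered by one clause: "Means will be compared among all the three arms using analysis of variance". The only adjustment mentioned follows the clause on proportions: "logistic regression will be used to analyze for confounding effects". No variables are listed for it.
- **Sample size.** The trial is sized by one-way ANOVA for a 1-point target and "our anticipated variance of 2", with 80% power at the 0.05 level. This gives 40 per arm, with 45 per arm to be enrolled.
- **Eligibility.** The relevant inclusion criterion begins "Scheduled to undergo primary, 1 or 2 level, posterior lumbar laminectomy with or without fusion", and an exclusion criterion is "Surgery involving more than 2 vertebral levels". The planned level is therefore fixed at scheduling.
- **Allocation.** In the operating room, "the circulating nurse will roll a die to randomly assign the patient to one of the three pain management groups". There is no stratification.
- **Interventions.** Level sets the Exparel preparation in the combination arm ("2 level patients – 20 mL Exparel diluted to 40mL + 30 mL bupivacaine 0.5% w/v solution") and in the Exparel-only arm ("1 level patients – 20 mL Exparel; 2 level patients – 20 mL Exparel diluted to 40 mL"). The bupivacaine-only arm gets 30 mL with no rule by level.

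The screening questionnaire in Appendix 1 asks whether lumbar surgery is scheduled, but not for how many levels.

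**The concern.** A baseline variable that is known before assignment, cannot be changed by treatment and plausibly predicts the outcome can sharpen the treatment comparison at almost no cost. Number of levels meets the first two conditions. On the third, the Background section names incision size and tissue damage among the reasons for severe pain after spine surgery. A link between surgical extent and pain is therefore plausible, but the documents put no number on it.

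Leaving level out gives up some precision if it does predict pain. Because the die roll is unstratified, chance differences in level between arms also go unadjusted, and the plan does not call for them to be tabulated. Naming the covariate in advance matters too: a model term chosen after the data are seen is a discretionary choice.

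**Working it through.** **Inputs from the documents.** Three arms, n = 40 per arm, 1-point target, variance 2 (taken as total variance), α = 0.05.

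**Assumptions.**
- Arm means are spread evenly over 1 point (0, 0.5, 1).
- The two-level share p is 20% or 50%. An 80% share gives the same power as 20%, since only p(1−p) enters.
- Two-level patients score d = 0 to 1 point higher, by the same amount in every arm.

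**Step 1: reproduce the plan's figure.** The noncentrality is λ = n·Σ(mean − grand mean)²/variance = 40 × 0.5/2 = 10. Power of F(2, 117) is 0.805. At 39 per arm it is 0.794. The stated 40 is the smallest n that reaches 80%.

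**Step 2: add level.** Residual variance is 2 − p(1−p)d², and error df fall from 117 to 116. Power was simulated with 200,000 trials per setting and level drawn independently of arm, so chance imbalance is included. The Monte Carlo standard error is √(0.8 × 0.2/200,000) = 0.0009.

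| d (points) | p = 20%: without / with level | p = 50%: without / with level |
|---|---|---|
| 0 | 0.805 / 0.802 | 0.804 / 0.801 |
| 0.25 | 0.804 / 0.802 | 0.804 / 0.804 |
| 0.5 | 0.805 / 0.810 | 0.806 / 0.815 |
| 1 | 0.805 / 0.835 | 0.807 / 0.857 |

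Type I error with level in the model is 0.050 to 0.051. The noncentral F formula, which ignores chance imbalance, gives 0.813 to 0.818 at d = 0.5 and 0.838 to 0.857 at d = 1.

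**Step 3: express the gain in patients.** Near 40 per arm, one more patient per arm adds about 0.010 power (0.805 to 0.815).
- At d = 0.5 the simulated gains of 0.005 and 0.009 equal about 0.5 to 0.9 patient per arm.
- At d = 1 the gains of 0.030 and 0.050 equal about 3 to 5 patients per arm.
- The variance formula 40 × 2/(2 − p(1−p)d²) gives slightly more, 40.8 to 41.3 and 43.5 to 45.7, because it ignores chance imbalance.

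**Step 4: pairwise contrasts.** The standard error of a difference between two arms is √(2 × residual variance/40). Without level this is √(4/40) = 0.316. With level at p = 50% it is √(2 × 1.9375/40) = 0.311 at d = 0.5 and √(2 × 1.75/40) = 0.296 at d = 1. The gain is therefore not tied to the omnibus test.

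**Step 5: size of chance imbalance.** The SD of the difference in two-level share between two arms is √(2p(1−p)/40), which is 0.089 at p = 20% and 0.112 at p = 50%. Multiplied by d, the shift in an arm difference has SD 0.045 to 0.056 points at d = 0.5 and 0.089 to 0.112 at d = 1. A given pair of arms differs by at least 4 of 40 two-level patients with probability 0.326 and 0.434 respectively.

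**Step 6: relax the common effect.** The Exparel preparation changes with level and the bupivacaine dose does not, so the level effect could differ by arm. With the level effect confined to the arm with the most pain (60,000 trials per setting), power without / with level is:
- 1 point: 0.802 / 0.799 at p = 20% and 0.805 / 0.809 at p = 50%
- 0.5 point: 0.804 / 0.800 and 0.804 / 0.803

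The gain essentially disappears.

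**Step 7: by-level estimates.** The 95% half-width of an arm difference within a level is 1.96 × √(4/n per arm at that level). This is 0.88 for n = 20, 0.69 for n = 32 and 1.39 for n = 8, against a 1-point target. Power for a 1-point arm-by-level interaction is 24% to 35%.

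**The case against.** The strongest reply is that nothing is broken. The ANOVA is valid, the contrast pooled over 1- and 2-level patients is the intended one, and the gain depends on a level effect that no section states. At 0.25 point or less there is no gain. The effect that makes a real difference, 1 point, is as large as the whole treatment target. If level matters in one arm only, the benefit vanishes. Other candidates have comparable support: the Background section also cites preoperative pain and preoperative opioid use, and fusion varies within the eligible population. All of this stands, and it is why the point is low priority.

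It is also fair that chance imbalance should not be made to sound alarming. Its SD of 0.045 to 0.056 at a 0.5-point effect is small beside a standard error of 0.316, which already allows for it.

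Some stronger readings are tempting but unsupported:

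- A reader might infer that omitting level, or diluting Exparel by level, biases the arm comparison. It does not. Assignment is random and independent of level, and the dilution rule is part of the treatments being compared.
- A reader might infer that the plan adjusts the pain score by logistic regression. The sentence does not tie that model to the pain score, and it would fit a binary outcome such as incidence of opioid-related events. It is fair to say only that no adjustment method suited to a continuous mean is specified.
- A reader might infer that the omnibus F test should be fixed as primary. The hypothesis is that the combination beats each single drug, so the choice of primary contrast is a separate question. The covariate serves either choice.

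**Conclusion.** The point holds as a cheap, low-priority improvement. The planned ANOVA is valid and the sample size is correct as stated. Under a level effect similar across arms, adding planned level moves power at 40 per arm from about 0.805 to 0.81 to 0.82 at 0.5 point, and to 0.83 to 0.86 at 1 point. If level does not predict pain, or does so in one arm only, the loss is at most about 0.005.

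These figures rest on assumed level effects and two-level shares, on variance 2 being the total variance, on evenly spread arm means and on 40 analysed in each arm. The documents do not show that level is the best available covariate. The case for it is that the protocol already uses it for eligibility and dosing, so it must be known before treatment.

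**What to change.** Add to the analysis text under Study Methodology:

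*Mean pain score will be analysed in a linear model with arm and planned number of levels (1 or 2, as scheduled and recorded before the die roll) as main effects. The primary arm comparison will be taken from this model. Number of levels will be tabulated by arm.*

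Use the scheduled level, not the level operated on. The dosing text does not say which of the two it means, and only the scheduled level is certain to precede assignment. Arm differences within each level are optional and should be labelled exploratory: they are imprecise and cannot separate infiltration volume from surgical extent.

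The cost is a short paragraph, one error degree of freedom (117 to 116), one table and one recorded data item, since Appendix 1 does not capture number of levels. Sample size stays at 40 analysed and 45 enrolled per arm, and the infiltration volumes do not change.
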